6.7 Study Intervention After the End of the Study

After a participant has completed the study or has withdrawn prematurely, usual treatment will be administered, if required, in accordance with the study site's SoC and generally accepted medical practice and depending on the participant's individual medical needs.

6.8 Special Precautions

- Participants should be carefully monitored for ophthalmological complications such as keratitis and corneal disorders according to local guidelines.
- Caution should be exercised with the intake of anticoagulants, phenytoin and/or leucovorin, and of drugs mainly metabolized by CYP3A with a narrow therapeutic index.
- Care should be exercised when capecitabine is coadministered with CYP2C9 substrates, e.g. phenytoin. Participants taking phenytoin concomitantly with capecitabine should be regularly monitored for increased phenytoin plasma concentrations.
- Participants taking coumarin-derivative anticoagulants concomitantly with capecitabine should be monitored regularly for alterations in their coagulation parameters (prothrombin time or international normalized ratio) and the anticoagulant dose adjusted accordingly.
- Capecitabine dosing should be discontinued in the event of severe mucocutaneous reactions. Capecitabine dosing should be interrupted in the event of hand-and-foot syndrome, hyperbilirubinemia, and low neutrophil or platelet counts.

Further details of special precautions for capecitabine are available in the Product Information/SmPC.

See Section 5.3.1 for dietary restrictions.

6.9 Management of Adverse Events of Interest

For peposertib no AEs of special interest have been defined so far. Specific toxicities identified during the conduct of the study will be closely monitored and specific instructions for monitoring and management of expected toxicities will be incorporated into the protocol and the Investigator's

Brochure. When further safety data for this study intervention combination become available, risk assessment and mitigation activities will be reviewed to assess the continued appropriateness.

The management of toxicity due to capecitabine administration is described in Section 6.6.3.2.

Toxicities related to RT will be managed according to the local institute's guidelines.

7 Discontinuation of Study Intervention and Participant Discontinuation/Withdrawal

7.1 Discontinuation of Study Intervention

The participant must be withdrawn from the study intervention in the event of any of the following:

- Therapeutic failure requiring urgent additional medication, such as administration of new anticancer therapy that is considered more suitable according to the Principal Investigator
- Discontinuation of RT if participant is unable to tolerate < 80% of the planned RT dose
- Adverse events that cause RT delays of > 7 days
- Occurrence of AEs, if discontinuation of study intervention is desired or considered necessary by the Investigator, or if after temporary treatment interruption the AE does not resolve or worsens in severity
- Pregnancy of participant
- Prohibited concomitant therapy (as defined in Section 6.5.1) where the predefined consequence is withdrawal from the study intervention
- Noncompliance that is deemed by the Investigator or the Sponsor to compromise participant safety or study integrity.

The SoA (Section 1.3) specifies the data to collect at study intervention discontinuation and follow-up, and any additional evaluations that need to be completed. Participants who discontinue study intervention must be followed on study including completion of study assessments, including at minimum tumor assessments until disease progression, until resolution of toxicity or discontinuation from study.

7.1.1 Temporary Discontinuation

Formal criteria for the dose modification, including temporary interruption where applicable, for capecitabine are provided in Section 6.6.3.2, and for peposertib and RT are provided in Section 6.6.3.3.

7.1.2 Rechallenge

Not applicable.

7.2 Participant Discontinuation/Withdrawal from the Study

- A participant may withdraw from the study at any time, at his/her own request or may be withdrawn at any time at the discretion of the Investigator for safety, behavioral, compliance, or administrative reasons.
- At the time of discontinuing from the study, if possible, a discontinuation visit will be conducted, as listed in the SoA. The SoA specifies the data to collect at study discontinuation and follow-up, and any additional evaluations that need to be completed.
- If the participant withdraws consent for future involvement in the study, any data collected up to that point may still be used, but no future data can be generated, and any biological samples collected will be destroyed.
- A participant has the right at any time to request destruction of any biological samples taken. The Investigator must document this in the site study records.

Participants should be explicitly asked at time of discontinuation of study if they would allow survival information to be collected including verification of medical/public records as permitted by local regulations. These responses should accordingly be captured in the participant's source data and reported in the eCRF accordingly.

The SoA (Section 1.3) specifies the data to collect at study discontinuation and follow-up, and any additional evaluations that need to be completed.

Participants who are discontinued/withdrawn from the study will not be replaced.

7.3 Lost to Follow-up

A participant will be considered lost to follow-up if he or she repeatedly fails to return for scheduled visits and is unable to be contacted by the study site.

The following actions must be taken if a participant fails to return to the clinic for a required study visit:

- The site must attempt to contact the participant and reschedule the missed visit as soon as possible, counsel the participant on the importance of maintaining the assigned visit schedule, and ascertain if the participant wants to or should continue in the study.
- Before a participant is deemed "lost to follow-up", the Investigator or designee must make every effort to regain contact with the participant: 1) where possible, make 3 telephone calls; 2) if necessary, send a certified letter (or an equivalent local method) to the participant's last known mailing address, and 3) if a participant has given the appropriate consent, contact the participant's general practitioner for information. These contact attempts should be documented in the participant's medical record.
- Should the participant continue to be unreachable, he/she will be considered to have withdrawn from the study.

8 Study Assessments and Procedures

- Study assessments and procedures and their timing are summarized in the SoA (Section 1.3).
- **No** protocol waivers or exemptions are allowed.
- Immediate safety concerns should be discussed with the Sponsor immediately upon occurrence or awareness to determine if the participant should continue or discontinue study intervention.
- Adherence to the study design requirements, including those specified in the SoA (Section 1.3), is essential and required for study conduct.
- All Screening evaluations must be completed and reviewed to confirm that potential participants meet all eligibility criteria. The Investigator will maintain a screening log to record details of all participants screened, to confirm eligibility, and if applicable, record reasons for screening failure.
- Prior to performing any study assessments that are not part of the participant's routine medical care, the Investigator will obtain written informed consent as specified in [Appendix 2](#) (Study Governance).
- Procedures conducted as part of the participant's routine medical care (e.g. blood count) and obtained before signing of the ICF may be used for Screening or baseline purposes provided the procedures met the protocol-specified criteria and were performed within the time frame defined in the SoA (Section 1.3).
- Regarding the visits from Week 7 to 14 during the short-term safety follow-up ([Table 1](#)). The Week 14 visit is mandatory as this is needed for restaging and evaluation. All other visits in this period are optional and needed only in case of acute toxicities until recovery to Grade 1 or baseline.
- A maximum of 255 mL of blood will be collected in any one-month period from each participant in the study, including any extra assessments that may be required.

Screening:

Participants will be screened between Days -28 and -1, prior to first dosing on Day 1. Assessments and procedures to be performed at Screening are detailed in the SoA (Section 1.3). Screening-specific procedures include:

- **Demography:** date of birth, sex (gender), race, and ethnicity.
- **Medical history:** disease history, previous illness and surgeries (e.g. all during the past year and only major ones prior to that), concomitant illness, relevant medication, allergies, therapies stopped or changed at entry into the study, tobacco use including pack years, and alcohol use.
- **Eastern Cooperative Oncology Group Performance Status:** assessed at Screening to assess eligibility (Section 5.1) and then assessed according to the SoA (Section 1.3).
- **Chest-abdominal computerized tomography (CT):** A CT scan of the chest and abdomen will be performed prior to the beginning of study intervention to document the baseline status of the participant. Computerized tomography will be performed with intravenous iodinated contrast unless contraindicated. Evaluation up to 28 days prior to start of study intervention is allowed.

In the case of a rescreen and the screening CT scan is > 28 days from the previous screening scan, the screening CT will need to be repeated.

- **DRE and endoscopy (and EUS if indicated or if performed):** for participants who have received induction chemotherapy prior to start of study

Surgery

Participants will undergo surgery using TME 15 weeks (\pm 14 days) after start of RT according to a standardized technique, unless there are contraindications for surgery ([Ridgway 2003](#), [Parfitt 2007](#)), if the participant refuses, or if the participant has a cCR and is eligible for organ preservation.

The choice of the surgical procedure, abdominoperineal resection or low anterior resection, is at the surgeon's discretion. Further details will be described in a dedicated surgical charter.

8.1 Efficacy Assessments and Procedures

8.1.1 Pathological Complete Response

The pathologic specimens after TME will be evaluated using standard pathological guidelines as described in the [Appendix 6](#). All surgical and pathology reports for the TME resection must be submitted.

The American Joint Committee on Cancer (AJCC) 8th edition ([Amin 2017](#)) will be used to categorize the completeness of the TME resection.

Reports must contain information about microscopic involvement and surgical resection margins. If there is residual macroscopic tumor, standard pathological examination will be carried out with 3 to 5 sections to investigate the deepest invasion in the bowel wall. If no macroscopic tumor is present and only a small ulcer is observed, the ulcer with a 2 cm margin will be examined for residual tumor and deepest invasion in the bowel wall. All lymph nodes will be examined according to standard procedures and the circumferential resection margin (CRM) will be measured ([Washington 2009](#)). The status of the surgical CRM will be defined as involved if there is tumor within 1 mm of the CRM.

The extent of residual tumor in the resected specimen will be classified according to the Tumor Node Metastases staging system of the 8th edition AJCC, with the prescript "y" to indicate that the tumor had been treated before surgical resection. After preoperative CRT, residual tumor masses will be semi-quantitatively evaluated according to the 4-point regression grading scale Modified Ryan scheme for tumor regression score (see [Appendix 6](#)).

A pCR will be defined as the absence of viable tumor cells in the primary tumor and lymph nodes (ypT0N0).

Standard data on pathology, completeness of resection, and the response to neoadjuvant chemotherapy will be collected. The slides will be locally reviewed to record whether there was

macroscopic clearance of the tumor. Assessments of the pathology must be according to international guidelines and will be further described in [Appendix 6](#).

8.1.2 Tumor Evaluation Methods and Response Assessment

Rectal cancer staging, and measurement at baseline and after chemoradiation should be performed as per NCCN Guidelines for Patients Rectal Cancer 2019. For participants who received induction treatment the baseline assessments will be based on MRI, endoscopy and DRE and biopsy, if required. For participants without induction treatment, the baseline assessment will consist of MRI only. For all participants the assessments after chemoradiation (Week 14) will include MRI, endoscopy and DRE and biopsy, if required. This is all based on a modification of tumor evaluation as described by [Maas 2015](#). Tumor assessments done during long-term Safety Follow-up will only include MRI (T_2 weighted and diffusion weighted) or CT scans ([Table 1](#) and [Table 2](#)).

Baseline assessments are to be taken not earlier than 4 weeks prior to study intervention start/randomization. After study intervention start/randomization, tumor assessments will be performed at 14 weeks (± 7 days) after study intervention start/randomization (i.e. before surgery) and 27 weeks (± 2 week) after study intervention start/randomization, every 3 months thereafter (± 2 weeks) until 1 year after study intervention start/randomization.

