Physical Examination	X	Physical examination (including body weight) will report findings in the irradiated area during Short- and Long-Term FU periods.
ECOG PS	X	
Adverse Event Assessment	X	Evaluation of ongoing or new AEs assessed as related to study intervention until resolution or permanent outcome. New SAE assessed as unrelated to study intervention only up to Wk 27.
Concomitant Therapy	X	
Adjuvant Chemotherapy	X	Adjuvant chemotherapy if given, according to local guidelines, must start between 1 and 3 mo after surgery.
Hematology	X	
Serum Chemistry and Coagulation	X	

Study Periods	Long-term Safety FU	Notes
Visit Weeks	19 to 52	
Visit Week	21 and 27 wk after start of study intervention/ randomization: Wk 21 and 27; thereafter every 3 mo in Yr 1: Wk 39 and 52	Participants followed-up until 1 year after start of study intervention/randomization, or earlier due to any reason whereby tumor assessments are no longer applicable (e.g. if new treatment is started, study discontinued, withdrawal of consent). Adjuvant chemotherapy is allowed as per local standards (see Section 6.5). Participants receiving adjuvant chemotherapy will continue to follow the schedule of activities as per protocol. If adjuvant chemotherapy is given any additional safety evaluations/laboratory tests will be as per local practice. Reason for early discontinuation should be captured in source documents. If EOT occurs before Wk 52, all assessments must be done as planned for Wk 52.
Visit Windows (Week)	± 1 for Wk 21; ± 2 for other visits	

Participants who have already been followed up for more than 1 year (Long-term Safety or Survival Follow-up) will be discontinued from the study after the approval of protocol amendment version 4.0 by the respective Health Authority and Ethics Boards. Participants will be informed of the discontinuation by the Investigator via a phone call. No further study visits or assessments are planned.

Assessment and Procedures

Carcinoembryonic Antigen	X	
CCI		
MRI/CT	X (starting Wk 27)	T ₂ weighted and diffusion weighted, without gadolinium. No MRI/CT at Wk 21.

AE=adverse event, CT=computerized tomography, ctDNA=circulating tumor DNA, DBP=diastolic blood pressure, ECOG PS=Eastern Cooperative Oncology Group Performance Status, EOT=End of Trial, FU=Follow-up, MRI=magnetic resonance imaging, SAE=serious adverse event, SBP=systolic blood pressure.

CCI

Table 4 Pharmacokinetic Sampling Schedule of Peposertib and Capecitabine

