total mesorectal excision [TME]), with the aim to remove the irradiated tumor and decrease the risk of local recurrence and mortality (National Comprehensive Cancer Network® [NCCN] Guidelines for Patients® Rectal Cancer 2019; Glynne-Jones 2017). This methodology has resulted in a decrease in local recurrence and an improvement in mortality rates (Shahab 2017). However, one-third of patients with locally advanced rectal cancer will later develop distant metastases and will subsequently die from the disease. In addition, most survivors experience significant impairment in their QoL, due primarily to removal of the rectum. Consequently, the current challenges in the treatment of locally advanced rectal cancer are how to improve survival by reducing the risk of distant metastases, and how to improve QoL in surviving patients by preserving the rectum. There is an unmet need to improve long-term outcomes and QoL and so the development of new therapeutic strategies to further increase these aspects is of key importance.

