In conclusion, emerging clinical safety data from studies EMR100036-001 and EMR100036-002, and supportive results of a comprehensive series of nonclinical safety pharmacology, PK, and toxicology studies, as well as primary and secondary PD findings support continued clinical development of peposertib in combination with RT, and/or chemotherapy.

3 Objectives and Endpoints

Study objectives and endpoints are provided in [Table 6](#). Statistical analysis of the endpoints is described in [Section 9.4](#).

Table 6 Study Objectives and Endpoints

Objectives	Endpoints (Outcome Measures)	Endpoints (Outcome Measures) Timeframe
Primary		
To define an MTD and RP2D of peposertib in combination with capecitabine and RT	Occurrence of dose limiting toxicities	Time from first study intervention to the end of CRT with a final assessment at 4 weeks after surgery
Secondary		
To evaluate safety and tolerability of peposertib in combination with capecitabine and RT	
 • Occurrence of TEAEs and treatment-related adverse events according to the NCI-CTCAE version 5.0 • Occurrence of abnormalities (Grade ≥ 3) in laboratory test values, markedly abnormal vital sign measurements, and clinically significantly abnormal ECGs including clinically important increases in QT interval (QTcF) 	Time from first study intervention to final assessment at 1 year
To explore antitumor activity of peposertib in combination with capecitabine and RT	
 • Composite endpoint of pCR/cCR • Disease-free Survival • pCR • cCR • Local recurrence and/or distant metastasis • Neoadjuvant rectal score 	
 • Pathology evaluation of specimen after surgery (pCR) and clinical evaluation 1 to 2 weeks prior to surgery (cCR) • Time from first study intervention to final assessment at 1 year • Pathology evaluation of specimen after surgery • Time from first study Intervention until clinical evaluation 1 to 2 weeks prior to surgery • Time from surgery to final assessment at 1 year • Pathology evaluation of specimen after surgery
To assess the PK of peposertib	PK profile of peposertib in terms of PK parameter estimates (e.g. C _{max} , AUC _{0-t} , t _{max} , CL/f, Vz/f, t _{1/2})	FD1 and FD9

CCI

cCR=Clinical Complete Response, CRT=chemoradiotherapy, CCI [REDACTED]
[REDACTED] ECG=electrocardiogram, FD=fraction day, MTD=maximum tolerated dose, NCI-CTCAE=National Cancer

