MRI-T2W	Increase in tumor size	
 • More intermediate than dark T2 signal, • no T2 scar AND/OR 
 • No regression of lymph nodes 	
 • Mostly dark T2 signal, • Some remaining intermediate signal AND/OR 
 • Partial regression of lymph nodes 	
 • Normal appearing bowel wall without any fibrosis in the tumor bed. • Only dark T2 signal, no intermediate T2 signal. • No visible lymph nodes or very few, small (< 5 mm nodes)

MRI=magnetic resonance imaging.

All participants, including those not undertaking surgery after chemoradiation are expected to continue loco-regional status evaluation (Table 17, MRI and optional Endoscopy/Digital), until progressive disease, at the frequency described in Section 8.1.2 and the SoA (Table 2) for Long-term Follow-up evaluations (Week 27, thereafter every 3 months in Year 1: Weeks 39 and 52).

Table 17 Response Criteria During Long-Term Safety Evaluation

Method	Progression	Complete Response
MRI-T2W or CT	
 • Local recurrence AND/ OR 
 • distant recurrence 	
 • No evidence of disease

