14.3 Secondary Endpoint: Local Recurrence and/or Distant Metastasis

Population: FAS analysis set (participants with surgery only)

Time from surgery to local recurrence will be defined as time from day of surgery to the date of the first documentation of progression of disease, flagged as 'local recurrence' or 'local recurrence and distant metastasis' ('TUMOR ASSESSMENT(ACCORDING TO NCCN) DURING LONG-TERM SAFETY AND SURVIVAL FOLLOW-UP' eCRF page).

Time from surgery to distant metastasis will be defined as time from day of surgery to the date of the first documentation of progression of disease, flagged as 'distant metastasis' or 'local recurrence and distant metastasis' ('TUMOR ASSESSMENT(ACCORDING TO NCCN) DURING LONG-TERM SAFETY AND SURVIVAL FOLLOW-UP' eCRF page). Only subjects who undergo rectal surgery (week 15) will be included in this analysis.

Table 8 Date of event / censoring definition for Local/Distant recurrence Analysis

	Status	Censoring	Date of event / censoring
Time to local recurrence: PD flagged as 'Local recurrence' or 'Local recurrence and distant metastasis'	No consecutive missing tumor assessments	Event	Date of progression
	After two or more subsequent missing tumor assessments (i.e. 2 times the scheduled time interval between two subsequent response assessments)	Censored	Date of last tumor assessment with outcome CR or date of surgery, whatever is later
Time to distant metastasis: PD flagged as 'Distant metastasis' or 'Local recurrence and distant metastasis'	Time to local recurrence: No consecutive missing tumor assessments and PD flagged as 'Distant metastasis'	Censored	Date of progression
	Time to distant metastasis: No consecutive missing tumor assessments and PD flagged as 'Local recurrence'		
No PD flagged as 'Local recurrence', 'Distant metastasis' or 'Local Recurrence and Distant metastasis' and no missed tumor assessment		Censored	Date of last tumor assessment with outcome CR or date of surgery, whatever is later

CR = Complete response; PD = Progressive disease

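### Follow-up scans need not cover the chest or abdomen, so distant metastases can go undetected while the SAP counts the participant as metastasis-free up to that scan.

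*Protocol*

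**What the plan says.** **Endpoint.** Protocol Section 3, Table 6 lists "Local recurrence and/or distant metastasis" as a secondary endpoint, from surgery to 1 year, and also disease-free survival (DFS). SAP 14.3 analyses time to distant metastasis separately from time to local recurrence.

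**Follow-up imaging.** Protocol 8.1.2: "Tumor assessments done during long-term Safety Follow-up will only include MRI" (T2- and diffusion-weighted), and the sentence goes on to allow CT scans instead. The MRI/CT row of the long-term schedule (Table 2) gives only MRI sequences in its note: "weighted and diffusion weighted, without gadolinium. No MRI/CT at Wk 21". Scans fall at Weeks 27, 39 and 52. No body region is stated.

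**Purpose and scoring.** Appendix 5 says that all participants, operated on or not, are "expected to continue loco-regional status evaluation (Table 17, MRI and optional Endoscopy/Digital" examination). Table 17, to which it refers, takes one MRI or CT and sorts the participant into progression (local, distant or both) or complete response.

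**Chest and abdomen.** Section 8 (Screening): "A CT scan of the chest and abdomen will be performed prior to the beginning of study intervention". No such scan is specified at any later visit.

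**Analysis.** For a participant without a recorded event, SAP Table 8 sets the censoring date as "Date of last tumor assessment with outcome CR or date of surgery, whatever is later". For DFS, SAP 14.2 counts any assessment whose result is not NE or NA as adequate. Neither rule depends on what was imaged.

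**The concern.** The endpoint needs information on distant sites, but the only evaluation that feeds it is described as loco-regional. A site can follow the schedule with rectal MRI at every visit. A complete response from such a scan then moves the distant-metastasis censoring date forward exactly as a chest and abdomen CT would. DFS uses the same progression assessments and has the same gap.

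The resulting error runs in one direction: undetected metastases make both curves look better. Its size follows local imaging habits. A reader of the Kaplan-Meier output cannot separate participants imaged and found clear from participants whose distant sites were not imaged. The protocol itself stresses this type of failure, noting in Section 2.2 that "one-third of patients with locally advanced rectal cancer will later develop distant metastases".

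**Working it through.** The plan ties no sample size, power or event count to this endpoint, so there is no figure to reproduce. The check traces the documents and then illustrates the size.

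**Tracing the rule**

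1. MRI or CT is accepted (8.1.2, Tables 2 and 17), so MRI alone complies.
2. Appendix 5 calls the evaluation loco-regional, and 8.1.2.1 describes the MRI in rectal terms (extramural vascular invasion, circumferential margin). A pelvic field is the natural reading, although it is not stated.
3. Section 8.1.2.2 records distant recurrence when a scan shows progression. Carcinoembryonic antigen and physical examination are done at follow-up visits, but no rule links an abnormal result to further imaging.
4. SAP Table 8 and SAP 14.2 then credit event-free time up to the scan.

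Counting from nominal Week 15 surgery, the scans fall at 27 − 15 = 12, 39 − 15 = 24 and 52 − 15 = 37 weeks. Up to 37 weeks can thus be credited as free of distant metastasis without the chest or upper abdomen having been imaged.

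**Illustrating the size**

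Inputs:
- n = 19, the number treated as of 06 May 2021 (Protocol 1.1). This is an upper bound for distant metastasis, because SAP 14.3 includes only participants with Week 15 surgery.
- r = true 1-year risk of distant metastasis. The documents give none, so 5%, 10%, 20% and one-third are assumed. The last is the protocol's background figure, which has no time horizon, and serves as an upper bound.
- m = share followed by loco-regional MRI only. Assumed 0, 0.5 or 1.
- o = share of metastases outside the MRI field. Assumed 0.9, varied from 0.7 to 1.0.

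Formulas:
- Expected missed events = n × r × m × o
- P(at least one missed) = 1 − (1 − r × m × o)^n
- Apparent metastasis-free proportion = 1 − r × (1 − m × o)

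Example with r = 0.10, m = 1, o = 0.9: missed = 19 × 0.10 × 1 × 0.9 = 1.71; P = 1 − (1 − 0.09)^19 = 0.83; apparent proportion = 1 − 0.10 × 0.1 = 0.99, against a true 0.90.

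| r | m | Missed (o = 0.9) | P(≥ 1 missed) | Apparent vs true metastasis-free |
|---|---|---|---|---|
| 5% | 0.5 | 0.43 | 0.35 | 97.3% vs 95% |
| 5% | 1 | 0.86 | 0.58 | 99.5% vs 95% |
| 10% | 0.5 | 0.86 | 0.58 | 94.5% vs 90% |
| 10% | 1 | 1.71 | 0.83 | 99.0% vs 90% |
| 20% | 0.5 | 1.71 | 0.83 | 89.0% vs 80% |
| 20% | 1 | 3.42 | 0.98 | 98.0% vs 80% |
| one-third | 0.5 | 2.85 | 0.95 | 81.7% vs 66.7% |
| one-third | 1 | 5.70 | 1.00 | 96.7% vs 66.7% |

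With m = 0 nothing is missed for this reason. Varying o from 0.7 to 1.0 gives 0.67 to 0.95 missed events at r = 10%, m = 0.5, and 2.66 to 3.80 at r = 20%, m = 1.

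**The case against.** The strongest reply is that the documents leave room for adequate imaging. CT is allowed everywhere. No text confines the MRI to the pelvis. Table 17 and Section 8.1.2.2 both ask for distant recurrence to be recorded. Section 8.1.2 refers to NCCN guidance for staging after chemoradiation, the SAP names the follow-up eCRF page after NCCN, and the SAP cites a tumor evaluation charter for cCR. None of these sources can be seen here. Carcinoembryonic antigen, examination or symptoms could also prompt other imaging. This stands as far as it goes: it means that metastases can be missed, not that they are.

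Second, the SAP already lists assessment method by visit, so MRI versus CT will be visible. That stands too, but body region is not listed.

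Third, the consequences are limited. No hypothesis is tested, the Kaplan-Meier analyses are descriptive, the primary endpoint is DLT, and Phase II will not start. This limits the weight of the point but does not remove it, because the estimates and their intervals will still be reported.

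Fourth, moving censoring back for participants without chest and abdomen imaging is one-sided. Their event-free time is dropped, while an event found by another route still counts, so the estimated event rate could be too high. This is right, and is why such a rule belongs in a sensitivity analysis and should not replace the main one.

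**Conclusion.** The point holds as a gap between the endpoint and what the schedule requires. The plan can credit metastasis-free time during which distant sites were never imaged, for both time to distant metastasis and DFS. The bias, if present, is favourable. Its size is unknown: from no missed events to about 3.4 for risks up to 20%, and up to 5.7 at the one-third upper bound, all with o = 0.9. These figures rest on assumed risk, modality mix and field coverage, and on 19 as the ceiling.

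Three stronger readings are tempting, and the documents do not support them:
- A reader might infer that follow-up is by MRI only and that lung or liver metastases are therefore certainly missed. CT is an explicit alternative and the MRI field is not stated.
- A reader might infer that every MRI-only complete response at Week 52 adds 37 weeks of false time. The credited time is false only for a participant who truly has undetected metastases, and only from their onset.
- A reader might apply the assumed rates to all 19 treated as the distant-metastasis denominator. SAP 14.3 restricts that analysis to participants operated on at Week 15, a number that is not given.

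**What to change.** Change the SAP only, before the 1-year follow-up analysis described in SAP 6.4.

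1. **Classify and report coverage.** From the listed assessment method and the filed scans or reports, classify each follow-up assessment by whether it covered chest and abdomen. Beside the distant-metastasis and DFS estimates, give the number and percentage of participants with such coverage at Weeks 27, 39 and 52.
2. **Add a sensitivity analysis** to SAP 14.2 and 14.3. Censor event-free participants at their last assessment that covered chest and abdomen. If there was none, censor at surgery for time to distant metastasis and at treatment day 1 for DFS. State that events found by other routes still count, so this version may overstate the event rate, and that it should be read together with the main analysis.
3. **Keep pelvic-only assessments for local recurrence** as now. Describe the unconditioned distant-metastasis estimate as no distant metastasis documented, not as participants known to be free of metastasis.

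Adding the baseline CT to Table 1 is not needed: Section 8 already requires it and enrolment is closed.

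Cost: SAP wording and a review of imaging reports for at most 19 participants, partly outside the eCRF because the assessment method does not show body region. No new scans are needed. The sensitivity analysis will have earlier censoring and wider intervals.
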